## 4.0 SUBJECT SELECTION

### 4.1 Inclusion Criteria

Patients must meet all of the following criteria to be eligible for study entry.

1. Men and women  $\geq 18$  years of age at the time of study entry.
2. Willing and able to provide written informed consent for the trial.
3. Life expectancy  $>12$  weeks.
4. Histologically or imaging confirmed hepatocellular carcinoma (mixed hepatocellular/cholangiocarcinoma or fibrolamellar subtypes are excluded).
5. Have disease that is not amenable for curative treatment approach.
6. Have measurable disease based on RECIST v1.1.
7.  $\geq 1$  liver lesions accessible for core biopsy that was either not previously treated by liver-directed therapy or progressed following liver-directed therapy.
8. Child-Pugh score of A.
9. ECOG performance status of 0 or 1.
10. Adequate hematology parameters:
  - a. Absolute neutrophil count (ANC)  $\geq 1000$  cell/mm $^3$
  - b. Platelet count  $\geq 50,000$ /mm $^3$
  - c. Hemoglobin (Hgb)  $\geq 8$  g/dL
11. Acceptable blood chemistry levels:
  - a. AST/SGOT, ALT/SGPT  $\leq 5$  x upper limit of normal (ULN)
  - b. Total bilirubin  $\leq 2$  ULN
  - c. Creatinine  $\leq 2$  x ULN
12. Subjects with active hepatitis B virus (Hep B) are allowed if antiviral therapy for hepatitis B has been given for  $>8$  weeks and viral load is  $<100$  IU/ml prior to first dose of trial treatment. Subjects with untreated hepatitis C virus (HCV) are allowed.
13. Willingness to undergo mandatory pre-treatment biopsy (unless there is adequate archival tumor specimen available) and mandatory on-treatment biopsy.

## 14. Criterion modified per Amendment v4.0.

- a. Women of child-bearing potential (WOCBP) must have a negative serum or urine pregnancy test (minimum sensitivity 25 IU/L or equivalent units of HCG) within 24 hr prior to planned treatment initiation.
- b. Women of childbearing potential (WOCBP) must agree to follow instructions for method(s) of contraception (Appendix 9) for the duration of treatment with study treatment(s) plus 5 months post-treatment completion (i.e., 30 days [duration of ovulatory cycle] plus the time required for nivolumab to undergo approximately 5 half-lives).
- c. Males who are sexually active with WOCBP must agree to follow instructions for method(s) of contraception for the duration of treatment with study treatment(s) plus 7 months post-treatment completion (i.e., 90 days [duration of sperm turnover] plus the time required for nivolumab to undergo approximately 5 half-lives). In addition, male participants must be willing to refrain from sperm donation during this time.
- d. Males who are sexually active with WOCBP must agree to use a latex or synthetic condom during sexual activity (see Appendix 4) for the duration of treatment with study treatment plus 7 months after the last dose of the study treatment (i.e., 90 days [duration of sperm turnover] plus the time required for nivolumab to undergo approximately 5 half-lives). This criterion applies to azoospermic males as well.
- e. Investigators shall counsel WOCBP, and male participants who are sexually active with WOCBP, on the importance of pregnancy prevention and the implications of an unexpected pregnancy. Investigators shall advise on the use of highly effective methods of contraception, which have a failure rate of < 1% when used consistently and correctly. Hormonal contraceptives are not considered highly effective methods of contraception for participants receiving BMS-986205 in this study who are WOCBP.

## 15. Ability to adhere to the study visit schedule and other protocol requirements.

## 16. Participants must be able to swallow pills intact.

#### 4.2 Exclusion Criteria

Patients who meet any of the following criteria will be excluded from study entry.

1. Received more than 1 prior systemic HCC-related therapy or currently receiving HCC-related systemic treatment or participating in a clinical trial and receiving study therapy.
2. Known history of positive test for human immunodeficiency virus (HIV) or known acquired immunodeficiency syndrome (AIDS).
3. Known diagnosis of immunodeficiency or active autoimmune disease or requiring systemic steroid equivalent of prednisone  $\geq$  10 mg/day or any immunosuppressive therapies  $\leq$  7 days of before the first dose of the study.
4. Active bacterial, viral (except Hepatitis B and C - see Inclusion Criterion 12), or fungal infection(s) requiring systemic therapy, defined as ongoing signs/symptoms related to the infection without improvement despite appropriate antibiotics, anti-viral therapy, anti-fungal therapy, and/or other treatment.
5. Active pneumonitis or history of interstitial lung disease (ILD) / pneumonitis requiring steroids.
6. Clinically significant ascites.
7. Hepatic encephalopathy.
8. Any significant medical condition including additional malignancies, laboratory abnormalities, or psychiatric illness that would prevent the subject from participating and adhering to study related procedures.
9. Live attenuated vaccine  $\leq$  30 days before the first dose of study treatment. Examples of live vaccines include, but are not limited to, the following: measles, mumps, rubella, chicken pox, yellow fever, rabies, *Bacillus Calmette-Guérin* (BCG), and typhoid vaccine. Seasonal influenza vaccines for injection are generally killed virus vaccines and are allowed; however, intranasal influenza vaccines (e.g., FluMist®) are live attenuated vaccines and are not allowed.
10. Use of strong inhibitor / inducer of CYP3A4 or CYP1A2.
11. Known history of surgery or medical condition that may affect drug absorption, per investigator discretion.
12. Participants with a history of G6PD deficiency or other congenital or autoimmune hemolytic disorders. All participants will be screened for G6PD deficiency prior to

enrollment using quantitative or qualitative G6PD assay results to suggest underlying G6PD deficiency.

13. Participants with a personal or family (i.e., in a first-degree relative) history or presence of cytochrome b5 reductase deficiency (previously called methemoglobin reductase deficiency) or other diseases that puts them at risk of methemoglobinemia. All participants will be screened for methemoglobin levels prior to enrollment using blood methemoglobin > ULN, assessed in an arterial or venous blood sample or by co oximetry.
14. Subjects with screening QTc interval > 480 ms.
15. Liver directed therapy  $\leq$ 4 weeks before the first dose of study.
16. History of esophageal or gastric variceal bleeding within 3 months of study enrollment.
17. Treatment with botanical preparations (e.g., herbal supplements or traditional Chinese medicines) intended for general health support or to treat the disease under study within 2 weeks prior to enrollment.
18. Prior history of serotonin syndrome.
19. Prior treatment with BMS-986205 or any other IDO1 inhibitors.
20. Women who are breastfeeding.
21. History or presence of hypersensitivity or idiosyncratic reaction to methylene blue.
22. History of allergy or hypersensitivity to any study treatment components, specifically to that of BMS-986205.
23. Participants who have had major surgery requiring general anesthesia or significant trauma who have not recovered per physician determination for at least 14 days prior to enrollment.
24. Participants who have had major surgery requiring general anesthesia or significant trauma who have not recovered per physician determination for at least 14 days prior to enrollment.
25. Participants with uncontrolled adrenal insufficiency.

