**Exclusion Criteria:**

1. Received more than 1 prior systemic HCC-related therapy or currently receiving HCC-related systemic treatment or participating in a clinical trial and receiving study therapy.

2. Known history of positive test for human immunodeficiency virus (HIV) or known acquired immunodeficiency syndrome (AIDS).
3. Known diagnosis of immunodeficiency or active autoimmune disease or requiring systemic steroid equivalent of prednisone  $\geq 10$  mg/day or any immunosuppressive therapies  $\leq 7$  days of before the first dose of the study.
4. Active bacterial, viral (except Hepatitis B and C - see Inclusion Criterion 12), or fungal infection(s) requiring systemic therapy, defined as ongoing signs/symptoms related to the infection without improvement despite appropriate antibiotics, anti-viral therapy, anti-fungal therapy, and/or other treatment.
5. Active pneumonitis or history of interstitial lung disease (ILD) / pneumonitis requiring steroids.
6. Clinically significant ascites.
7. Hepatic encephalopathy.
8. Any significant medical condition including additional malignancies, laboratory abnormalities, or psychiatric illness that would prevent the subject from participating and adhering to study related procedures.
9. Live attenuated vaccine  $\leq 30$  days before the first dose of study treatment. Examples of live vaccines include, but are not limited to, the following: measles, mumps, rubella, chicken pox, yellow fever, rabies, *Bacillus Calmette-Guérin* (BCG), and typhoid vaccine. Seasonal influenza vaccines for injection are generally killed virus vaccines and are allowed; however, intranasal influenza vaccines (e.g., FluMist®) are live attenuated vaccines and are not allowed.
10. Use of strong inhibitor / inducer of CYP3A4 or CYP1A2.
11. Known history of surgery or medical condition that may affect drug absorption, per investigator discretion.
12. Participants with a history of G6PD deficiency or other congenital or autoimmune hemolytic disorders. All participants will be screened for G6PD deficiency prior to enrollment using quantitative or qualitative G6PD assay results to suggest underlying G6PD deficiency.

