## **2.0 STUDY OBJECTIVES**

### **2.1 Primary Objective**

1. To obtain the safety and tolerability of BMS-986205 in combination with nivolumab in unresectable / metastatic HCC in the first or second line setting using CTCAE V5.0 criteria.
2. To determine efficacy as defined by objective response rate (ORR) of BMS-986205 in combination with nivolumab in unresectable / metastatic HCC in the first or second line setting using RECIST (version 1.1).

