### **5.5.3 Protocol-Specific Recommendation for Management of Hepatic Events**

Subjects with advanced HCC generally have underlying cirrhosis with decreased hepatic function. They may also have a concomitant chronic viral infection. For this study, the upper limits for inclusion were therefore adjusted to account for baseline liver dysfunction. Subjects with AST or ALT elevations within the CTCAE Grade 2 range are allowed to enroll in the study. This requires a protocol-specific approach for the management of hepatic events outlined as follows:

- Both BMS-986205 and nivolumab should be delayed for
  - Grade  $\geq 2$  toxicity in subjects with baseline AST or ALT within normal limit,
  - Grade  $\geq 3$  toxicity in subjects with baseline AST or ALT within grade 1 toxicity range
  - Drug related increase in AST or ALT at 2x baseline value or when AST or ALT is 8x ULN (whichever is lower) in subjects with baseline AST or ALT in grade 2 toxicity range.
- If AST or ALT levels do not improve with a dose delay of 3 - 5 days or if the levels worsen, initiate steroid therapy at 0.5 - 2 mg/kg/day methylprednisolone or oral equivalent.
- For ALT or AST levels  $> 8x$  ULN, initiate steroid therapy promptly at 1 - 2 mg/kg/day methylprednisolone or oral equivalent
- For all subjects initiating steroids, consult the PI within 24 hours after initiation of steroids. Gastroenterology consult is recommended.
- If AST or ALT levels do not improve within 3- 5 days or the levels worsen after the start of steroid therapy, discuss with the PI the possibility of adding mycophenolate mofetil at 1 g BID.
- Tapering of steroids can start once AST or ALT levels have declined by one CTCAE grade. Taper steroids slowly over no less than 1 month.

As outlined in above, nivolumab and BMS-986205 therapy may resume when AST or ALT have returned to patient's baseline unless the criteria for permanent discontinuation are reached. Subjects who require delay of therapy should be re-evaluated weekly or more frequently if clinically indicated. It is recommended to monitor elevations in AST or ALT approximately every 3-5 days until levels peak or begin to decline. Both therapies can be resumed when re-treatment criteria are met. The PI must be consulted prior to resuming nivolumab for all subjects who required steroid intervention. Tumor assessments for all subjects should continue as per protocol even if study drug dosing is delayed.

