## 9.0 CONCOMITANT AND EXCLUDED THERAPIES

### 9.1 Concomitant Therapy

The patient must be told to notify the investigational site about any new medications he/she takes after the start of the study drug. All medications (other than study drug) and significant non-drug therapies (including blood transfusions) administered during the study should be recorded.

Concomitant therapy includes any prescription medications or over-the-counter preparations used by a patient between the 7 days preceding the screening evaluation and the treatment discontinuation visit. Medications taken within 14 weeks prior to study treatment administration must be recorded on the case report form (CRF). Document vaccine use for 30 days prior to first dose of study drug.

Patients who experience infusion-associated symptoms may be treated symptomatically with antipyretics (ibuprofen preferred), diphenhydramine, and/or famotidine or another H2 receptor antagonist, as per standard practice. Serious infusion-associated events manifested by dyspnea, hypotension, wheezing, bronchospasm, tachycardia, reduced oxygen saturation, or respiratory distress should be managed with supportive therapies as clinically indicated (e.g., supplemental oxygen and  $\beta_2$ -adrenergic agonists).

Systemic corticosteroids and TNF $\alpha$  inhibitors may attenuate potential beneficial immunologic effects of treatment but may be administered at the discretion of the treating physician. If feasible, alternatives to corticosteroids should be considered. Premedication may be administered for Cycles  $\geq 2$  at the discretion of the treating physician. The use of inhaled corticosteroids and mineralocorticoids (e.g., fludrocortisone) for patients with orthostatic hypotension or adrenocortical insufficiency is allowed. Megastrol administered as appetite stimulant is acceptable while the patient is enrolled in the study.

Patients who use hormone-replacement therapy, prophylactic or therapeutic anticoagulation therapy (such as low-molecular-weight heparin or warfarin at a stable dose level), or other allowed maintenance therapy should continue their use, unless prohibited.

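### Exclusion 1 sets no minimum interval after prior systemic therapy and no recovery condition, so late effects of a just-stopped drug can enter the DLT count and shift the AST/ALT delay and resumption rules.

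*Combined protocol and SAP*

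**What the plan says.** Exclusion 1 reads "Received more than 1 prior systemic HCC-related therapy or currently receiving HCC-related systemic treatment or participating in a clinical trial and receiving study therapy", and the synopsis has the same rule. It caps prior lines at one and excludes patients on treatment now, whether routine or in another trial. It does not address how recently treatment stopped.

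Other exclusions in Section 4.2 do set times:
- Exclusion 15 covers liver-directed therapy in the "4 weeks before the first dose of study".
- Exclusion 17 covers botanicals "intended for general health support or to treat the disease under study within 2 weeks prior to enrollment".
- Exclusion 9 sets 30 days for live vaccines.
- Exclusion 3 sets 7 days for steroids and other immunosuppressives.
- Exclusion 23 sets 14 days for recovery from surgery or trauma.

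The only drug class barred by history is in exclusion 19: "Prior treatment with BMS-986205 or any other IDO1 inhibitors". Previously treated patients are in the target population, since Section 2.1 names "unresectable / metastatic HCC in the first or second line setting using CTCAE V5.0 criteria". Section 9.1 asks for 14 weeks of earlier medication to be recorded but attaches no eligibility consequence. Section 9.2 prohibits anticancer treatment during the study, not before it.

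**The concern.** Phase I has to attribute early toxicity to the combination in very few patients. Section 1.3.1 says the 50 mg starting level was chosen to observe liver toxicity in this population. One DLT in the first three patients changes the cohort decision, and Section 3.0 halts the study if 50 mg is not tolerated. If the previous drug was stopped days earlier, its late effects fall in the same weeks.

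The timing rules look like a gap, not a choice: a herbal product taken for the cancer triggers an interval and a systemic anticancer drug does not. The protocol also follows its own drugs for 100 days after the last dose (Sections 5.4 and 7.0), so it accepts that drug effects outlast dosing.

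**Working it through.** **The plan's own design figure.** Section 14.2 states 80% power at one-sided 0.05 for response rates of 5% versus 25%. The rule is at least 1 response in 9 to continue and at least 3 in 17 for success. The exact probability of success is the sum over x ≥ 1 of P(X = x; n = 9, p) × P(Y ≥ 3 − x; n = 8, p). This gives 0.0466 at p = 5% and 0.812 at p = 25%. The stated figures reproduce, and this point does not change them.

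**How carry-over reaches the DLT count.**
1. Section 15.1 defines an adverse event as something new or a worsening, so stable residual toxicity does not count. Late-onset or worsening effects do.
2. In Section 5.6 the general bullet for Grade 3 or higher toxicity outside skin, liver and blood has no drug-related qualifier. This is the widest route. Its listed exceptions, such as Grade 3 fatigue and short-lived nausea, vomiting or diarrhea, narrow it.
3. Bullets that do require drug-relatedness, including the hepatic one, are reached only through attribution. The Possibly Related category in Section 15.1.2 includes events that other drugs could also explain.
4. Prior anti-PD-1 therapy is not excluded. Section 4.1 (criterion 14b) builds 5 months from 30 days plus about five nivolumab half-lives, which leaves roughly 4 months of residual exposure. That exceeds both DLT windows the protocol gives: 6 weeks in Section 5.6 and 56 days in Section 3.0, two figures that themselves need reconciling.

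**How it reaches the hepatic rules.** In Section 5.5.3 the delay trigger depends on baseline AST/ALT: Grade 2 or higher from a normal baseline, and Grade 3 or higher from a Grade 1 baseline. For a Grade 2 baseline it is "Drug related increase in AST or ALT at 2x baseline value" or 8x ULN, whichever is lower. Resumption is tied to return to baseline. A prior drug that raises AST/ALT can therefore change the delay rule and raise the resumption target.

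The effect is bounded. Entry is capped at 5x ULN, where doubling would give 2 × 5 = 10x ULN, but the trigger stops at 8x ULN. The cap binds for any baseline above 8/2 = 4x ULN. The hepatic DLT limits in Section 5.6 and the AST/ALT discontinuation limits in Section 5.5.3 are fixed ULN multiples, so an AST/ALT baseline does not move them.

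Section 10.0 allows screening laboratory tests up to 14 days and scans up to 28 days before registration, so both can precede the last prior dose.

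**Illustrative size.** Let p be the true DLT rate, f the share of patients recently pretreated and c the added event risk in those patients. All three are assumptions.

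q = 1 − (1 − p)(1 − f·c)

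Under Section 14.1, level 1 clears with 0 of 3 DLTs, or with 1 of 3 followed by 0 of 3:

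P(clear) = (1 − q)³ + 3q(1 − q)² × (1 − q)³

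Example with p = 0.10, f = 0.5, c = 0.05: q = 1 − 0.90 × 0.975 = 0.1225, and P = 0.6757 + 0.2830 × 0.6757 = 0.867.

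| p | Share recently pretreated | c = 0 | c = 5% | c = 10% |
|---|---|---|---|---|
| 10% | half | 0.906 | 0.867 | 0.824 |
| 10% | all | 0.906 | 0.824 | 0.730 |
| 20% | half | 0.709 | 0.665 | 0.622 |
| 20% | all | 0.709 | 0.622 | 0.536 |

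**The case against.** The strongest reply is that existing safeguards cover most of this. Baseline symptoms are documented, only new or worsening events count, most other DLT bullets require drug-relatedness, and AST/ALT is capped at entry. The previous 14 weeks of medication are on record, and Section 17.2 requires a toxicity review meeting before the next dose level. AST/ALT baseline is not defined as the screening value, and biochemistry is repeated on Day 1 of each cycle, so a value taken on the earlier drug need not be the one used. All of this stands and narrows the consequence. None of it is an interval or a recovery condition, and the undefined baseline is itself a reason to specify one.

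Three stronger readings are tempting, and the documents do not support them.
- A reader might infer that any residual toxicity becomes a DLT, or that hepatic DLT limits shift with baseline. The adverse event definition and the fixed ULN multiples rule this out.
- A reader might apply 15% carry-over to every patient under the at-most-1-of-6 rule. Then q = 1 − 0.90 × 0.85 = 0.235, and the pass probability falls from 0.886 to 0.570. The arithmetic is right, but no rate in the documents supports 15%. First-line patients have no prior systemic drug, and level 1 can clear on 0 of 3.
- A reader might conclude that baseline tissue must also follow the last prior dose. Inclusion 13 and the study calendar accept archival tissue, and such a rule could force extra biopsies.

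**Conclusion.** The omission is real in both the synopsis and Section 4.2, and no other section fills it. Applied as written, eligibility admits a patient who stopped a systemic drug the day before registration. The consequence is limited to two routes: new or worsening events counted as DLTs, mainly through the unqualified Grade 3 or higher bullet, and a changed hepatic delay rule with a higher resumption target.

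At a true DLT rate of 10%, the loss in the chance of clearing level 1 is about 0.04 to 0.08 with half the patients recently pretreated (0.906 to 0.867 or 0.824). It is about 0.08 to 0.18 with all of them (0.906 to 0.824 or 0.730). These figures rest on assumed carry-over risks of 5% and 10%, an assumed pretreated share and independent events, so they show direction and rough scale only. The Phase II error rates are unaffected. This is a cheap improvement, not a flaw that invalidates the design.

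**What to change.** Amend exclusion 1 in Section 4.2 and the synopsis, in the form already used for exclusion 15:
- State a minimum interval between the last prior systemic or investigational anticancer dose and the first study dose.
- Add a condition that toxicity from that therapy has recovered to a stated level. The sponsor should set both the interval and the grade.
- Require baseline laboratory values and the baseline scan to be taken after that last dose, and define the AST/ALT baseline used in Section 5.5.3 accordingly.
- Leave the archival-tissue allowance as it is.

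The cost is amendment wording and a short wait for some second-line patients; a scan or blood test already taken on the earlier drug would need repeating. The missing attribution wording in the general DLT bullet is a separate matter that this change does not repair.

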#### **4.3 Inclusion of Women, Minorities, and Other Underrepresented Populations**

Recruitment is open to all minorities and both genders. Although distributions may vary by disease type, our recruitment procedures have been developed to enroll patients who are representative of the respective target population.

